## 2.3 Study Endpoints

### 2.3.1 Phase 1b Multiple Ascending Dose Safety

The primary endpoint is safety. Safety will be evaluated by presenting summaries of the following:

- Treatment-emergent adverse events (TEAEs), which are defined as adverse events (AEs) occurring after the first dose of study drug through TOC for study drug (Day 12) or through EOS for serious AEs (SAEs);
- Vital signs; and
- Clinical laboratory evaluations.

The endpoints listed for Phase 2a may be assessed as secondary endpoints in the safety cohorts; however, these cohorts are exploratory and not powered for any efficacy variable.

### 2.3.2 Phase 2a Endpoints

The Phase 2a endpoints are the following:

- Time to reach a National Early Warning Score 2 (NEWS2) score  $\leq 2$  maintained for at least 24 hours or hospital discharge (whichever comes first) for subjects on active drug versus placebo
- Clinical Improvement or response at TOC for study drug (Day 12)
- Proportion of subjects reaching a NEWS2 score  $\leq 2$  maintained for at least 24 hours or hospital discharge (whichever comes first) for subjects on active drug versus placebo at TOC for study drug (Day 12)
- Microbiological outcome at EOT for study drug (Day 5)
- Clinical Improvement or response at TOC for BAT (7 days [ $\pm 1$  day] after the end of BAT)
- Clinical Improvement or response at EOS (28 days after the end of BAT)
- Time to death
- NEWS2 score while hospitalized by study day
- Late composite efficacy, as defined by the following:
  - Survival at EOS (Days 39 to 81); and
  - No evidence of microbiological failure, as defined by either of the following:
    - Blood cultures that remain positive for SA  $\geq 7$  days from randomization; or
    - Isolation of SA from the blood or another sterile site (e.g., joint fluid, tissue)  $> 14$  days from randomization.
- Microbiological failure or relapse by any of the following:
  - Blood cultures that remain positive for SA  $\geq 7$  days from randomization;
  - Isolation of SA from the blood or another sterile site (e.g., joint fluid, tissue)  $> 14$  days from randomization; or
  - Blood culture positive for SA  $> 72$  hours after the first blood cultures showing clearance of SAB (defined as 2 consecutive days with negative SA blood cultures).

- Time to initial resolution of SAB
- Time to hospital discharge (and time to hospital discharge readiness)
- Need for and duration of intensive care unit (ICU) stay
- Need for and duration of endotracheal mechanical ventilation
- Need for and duration of noninvasive pressure ventilation (e.g., Continuous Positive Airway Pressure, Bilevel Positive Airway Pressure)
- PK of AP-SA02 with IV administration
- Relationship between AP-SA02 exposures and safety and efficacy endpoints
- Immunogenicity of AP-SA02 at EOS
- Time to resolution of any signs and/or symptoms of bacteremia present at Screening
- Time to resolution of any signs/symptoms related to focal site of SA infection (e.g., joint pain; redness; swelling; weight-bearing, back pain; weight-bearing, skin redness; drainage) from randomization on Day 1
- TEAEs, which are defined as AEs occurring after the first dose of study drug through TOC for study drug (Day 12) or through EOS for SAEs
- Proportion of subjects with acute kidney injury (AKI), defined as stage 1 or higher using modified Risk-Injury-Failure-Loss-End-stage renal disease (RIFLE) criteria at any time within the first 7 days or new need for renal replacement therapy between Day 1 and EOS
- Vital signs
- Clinical laboratory evaluations
- Change in C-reactive protein (CRP) from baseline to EOS
- Change in interleukin-10 from baseline through TOC for study drug (Day 12)
- Change in SA isolate sensitivity to AP-SA02 between initiation of study drug and the last isolation of SA from a sterile site (blood, joint fluid, tissue)
- Change in SA isolate susceptibilities to anti-staphylococcal antibiotics from baseline
- Change in SA isolate susceptibility to BAT from baseline; and
- Clinical and microbiological outcomes by foci of infection.

### 3 STATISTICAL METHODOLOGY

#### 3.1 General Considerations

##### 3.1.1 Analysis Day

Analysis day will be calculated from the date of first dose of study drug. The day of the first dose of study drug will be Day 1, and the day immediately before Day 1 will be Day -1. There will be no Day 0.

### 3.1.2 Definition of Baseline

Baseline is defined as the last non-missing value prior to the first dose of study drug. If a subject was randomized but not treated, the baseline value is last non-missing value on or prior to randomization date. Baseline SAB is defined as SA isolated from positive blood culture within 72 hours prior to first dose of study treatment. Blood culture results are obtained from local microbiology laboratories.

Any eligibility protocol deviation from the 72-hour blood culture timepoint (relative to randomization) will be discussed and approved for individual subject inclusion in the per protocol MITT population before database lock.

### 3.1.3 Summary Statistics

Categorical data will generally be summarized with counts and percentages of subjects. The denominator used for the percentage calculation will be clearly defined. Continuous data will generally be summarized with descriptive statistics including n (number of non-missing values), mean, median, standard deviation, minimum, and maximum.

All data will be listed by subject based on randomized subjects.

### 3.1.4 Hypothesis Testing

No formal testing will be done.

### 3.1.5 Handling of Dropouts and Missing Data

In cases of incomplete dates for AEs and concomitant medications, the missing component(s) will be assumed as the most conservative value possible. No imputation of start/end dates or times will be performed.

- If a medication date is missing or partially missing and it cannot be determined whether it was taken prior or concomitantly, it will be considered a concomitant medication.
- If the partial AE onset date information does not indicate that the event started prior to or after the treatment, the event will be classified as treatment emergent.

## 3.2 Analysis Populations

### 3.2.1 Intent-to-Treat Population (Efficacy Population 1)

The Intent-to-Treat (ITT) Population is defined as all randomized subjects in Phase 1b and Phase 2a who receive at least 1 dose of study drug. This will not include individuals that screen failed or were randomized but did not receive phage or placebo - at least one dose of phage or placebo must have been received.

### 3.2.2 Per Protocol Microbiological Intent-to-Treat (MITT) Population (Efficacy Population 2)

The Per Protocol MITT Population is defined as all subjects in the ITT population and enrolled in Phase 2a with baseline SAB and who receive at least 4 initial doses of study drug (placebo or phage). All protocol deviations for inclusion and exclusion will be determined prior to database lock and documented in the TMF.

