4.1 Inclusion Criteria

Inclusion criteria for Phase 1b and 2a

Subjects who meet all of the following criteria will be eligible to participate in the study:

1. Is able and willing to provide written informed consent or have consent provided by an LAR;
2. Is a hospitalized male or female adult subject aged 18 years or older at time of consent;
3. Has SAB identified from at least 1 blood culture or from a rapid diagnostic test within 72 hours of randomization. Time of positive blood culture starts from when specimen is collected for blood culture;
4. Has a plan for source control within 3 days after randomization to be completed within 7 days of randomization if relevant (eg, abscess drainage, washout or debridement of infected material) or has source already controlled;
5. If an FCBP, the subject must agree to use a highly effective method of birth control (defined as those, alone or in combination, that result in a low failure rate [ie, less than 1% per year]) from Day 1 through 60 days following the last dose of study drug;

Note: FCBP must have a negative serum pregnancy test within 72 hours prior to randomization. An FCBP is any female, regardless of sexual orientation, who meets the following criteria: has not undergone a hysterectomy or bilateral oophorectomy, or has not been naturally postmenopausal for at least 12 consecutive months (ie, has had menses at any time in the preceding 12 consecutive months).

6. If a male subject, the subject must agree to use barrier contraception (ie, condoms) from Day 1 through 60 days following the last dose of study drug;

Additional inclusion criteria for Phase 2a only

7. Has at least 1 of the following signs/symptoms at or within 72 hours prior to randomization:
 - a. Documented temperature $\geq 38.0^{\circ}\text{C}$ (100.4°F) or $\leq 36.0^{\circ}\text{C}$ (96.8°F) measured orally, $\geq 38.5^{\circ}\text{C}$ (101.3°F) or $\leq 36.5^{\circ}\text{C}$ (97.7°F) measured tympanically, or $\geq 39^{\circ}\text{C}$ (102.2°F) or $\leq 37^{\circ}\text{C}$ (98.6°F) measured rectally;
 - b. Heart rate >90 beats per minute;
 - c. Respiratory rate >20 breaths per minute;
 - d. White blood cell count $\geq 12.0 \times 10^9$ cells/L or $\leq 0.4 \times 10^9$ cells/L, or $\geq 10\%$ immature neutrophils;
 - e. Systolic blood pressure <90 mmHg; and/or
 - f. Pain associated with focal site of infection.

8. Has at least 1 of the following:

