9 STATISTICS

9.1 Analysis Populations

The following analysis populations will be defined for the Phase 1b and Phase 2a cohorts:

- Intent-to-Treat (ITT): all randomized subjects regardless of whether or not study drug is received;
- Phage-Sensitive ITT: all randomized subjects who receive both BAT and study drug, and whose SA isolate is sensitive to at least 1 of the phage components that comprise the study drug;
- Safety: all randomized subjects who receive at least 1 dose of study drug;
- MITT: all subjects in the ITT Population with baseline SAB and who receive at least 1 dose of study drug; and
- PK: all subjects (enrolled at predetermined/qualified PK sites) who have at least 1 PK sample drawn.

An SAP will be prepared and finalized before database lock and analyses of data. Summary data will be tabulated and presented by treatment group.

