### 2.2.4 Sample Size Determination

The study will enroll approximately 50 eligible subjects. Enrollment may be expanded up to a total of approximately 100 subjects to ensure that at least 8 treated and 4 placebo Phase 2a subjects are MRSA subjects and to account for additional subjects and cohorts that may be enrolled based on DRC review and Sponsor input based on emerging data. To ensure that at least 8 treated and 4 placebo Phase 2a subjects are MRSA subjects, no more than approximately 70 non-MRSA subjects will be enrolled without a protocol amendment.

The Phase 1b MAD safety cohorts will follow a standard 3 + 1 design for 2 cohorts (n = 4 for each cohort for a total of 8 subjects). However, additional cohorts (up to 3) may be added or existing cohorts expanded per recommendation of the DRC or Sponsor decision. The total sample size in Phase 1b may be increased up to a total of 20 subjects without a protocol amendment in consultation with the DRC.

Phase 2a will have an initial sample size of approximately n = 42 with a study drug to placebo allocation of 2:1 in order to enroll at least 38 subjects meeting the Microbiological Intent-to-Treat (MITT) Population criteria with the assumption that approximately 90% of randomized subjects will satisfy the MITT Population criteria. This will provide at least 80% power to detect a difference of 50% in the proportion of subjects in each treatment arm, with a 30% placebo portion meeting all conditions for Clinical Improvement or response at TOC for study drug (Day 12) in the MITT Population with a type 1 error rate of 0.05 (1-sided) using Fisher's exact test. Additional subjects may be included in Phase 2a after a protocol amendment.

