### 3.2.3 Phage Persistence and Clearance Population (Efficacy Population 3)

All subjects in Phase 1b and Phase 2a who have at least 1 PK sample drawn and received at least 4 initial doses of study drug will be divided into one of the following:

- Phage Persistence Population: defined as viable phage recovered at 3 hours post first administration of study drug
- Phage Clearance Population: defined as viable phage no longer recovered at 3 hours post first administration of study drug

Phage Persistence and Phage Clearance Population will be reported by the Sponsor separately. Subject lists for Phage Persistence Population and Phage Clearance Population will be provided by Sponsor for analysis.

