### 3.4 Efficacy Assessment

Efficacy data will be analyzed for ITT population, Per Protocol MITT population, Phage Persistence and Clearance population, and Phage-Sensitivity ITT population (if needed):

- Efficacy analysis performed using ITT population and Phase-Sensitivity ITT population (if needed) will be summarized by pooled treatment versus pooled placebo for Phase 1b and Phase 2a:
  - Phase 1b (uncomplicated SAB) vs Phase 1b placebo
  - Phase 2a (complicated SAB) vs Phase 2a placebo
- Efficacy analysis performed using Per Protocol MITT population will be summarized by pooled treatment versus pooled placebo for Phase 2a:
  - Phase 2a vs Phase 2a placebo.
- Efficacy analysis performed using Phage Persistence and Clearance population will be summarized by following:
  - Combination of Phase 1b (excluding cohort 1) and Phase 2a Persistence vs Combination of Phase 1b (excluding cohort 1) and Phase 2a Clearance vs Combination of Phase 1b placebo (excluding cohort 1) and Phase 2a placebo
  - Phase 2a Persistence vs Phase 2a Clearance vs Phase 2a placebo

Combination of Phase 1b placebo (excluding cohort 1) and Phase 2a placebo includes Phase 1b placebo (excluding cohort 1) and Phase 2a placebo in the ITT population. Phase 2a placebo includes Phase 2a placebo in the ITT population.

Phage Persistence and Phage Clearance Population and Phage-Sensitivity ITT population (if needed) will be reported by the Sponsor separately. Subject lists for Phage Persistence and Phage Clearance Population and Phage-Sensitivity ITT population (if needed) will be provided by Sponsor for analysis.

The endpoints in section 3.4.1 for Phase 1b and Phase 2a may be assessed as secondary endpoints.

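### No SAP population matches the MITT set named in the power statement, two 72-hour clocks conflict, and the Persistence/Clearance comparison removes early stoppers from the active side only

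*SAP*

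**What the plan says.** **Populations.** Protocol 9.1 gives "MITT: all subjects in the ITT Population with baseline SAB and who receive at least 1 dose of study drug". The sample-size text (Protocol 9.2.6, repeated in SAP 2.2.4) assumes that about 90% of 42 randomized subjects, at least 38, meet the MITT criteria. It claims at least 80% power for Day 12 clinical response in that population, "with a type 1 error rate of 0.05 (1-sided) using Fisher's exact test".

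SAP 3.2.2 defines only a Per Protocol MITT: Phase 2a subjects "with baseline SAB and who receive at least 4 initial doses of study drug (placebo or phage". SAP 3.2.1 keeps an ITT set with a one-dose rule but without baseline SAB. Protocol 7.2 ties three endpoints to MITT, Day 12 response among them; SAP 2.3.2 omits that link. SAP Section 6 records that the population definitions were updated, without a reason.

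**Clock.** Protocol 4.1 admits a subject who "Has SAB identified from at least 1 blood culture or from a rapid diagnostic test within 72 hours of randomization". SAP 3.1.2 states: "Baseline SAB is defined as SA isolated from positive blood culture within 72 hours prior to first dose of study treatment". The same section adds: "Any eligibility protocol deviation from the 72-hour blood culture timepoint (relative to randomization) will be discussed and approved for individual subject inclusion". It gives no criterion for approval.

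**Persistence and Clearance.** Under SAP 3.2.3 these subjects must "have at least 1 PK sample drawn and received at least 4 initial doses of study drug". For their comparator, SAP 3.4 says that "Phase 2a placebo includes Phase 2a placebo in the ITT population", and the pooled Phase 1b/2a comparison uses ITT placebo likewise. SAP 3.6 repeats both for the pharmacodynamic endpoints.

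**The concern.** The power claim names a population that the SAP no longer analyzes, and the 90% and 38 figures were not revisited when the dose rule changed.

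Reaching dose 4 happens after randomization and treatment can affect it. With dosing every 6 hours, dose 4 falls 3 × 6 = 18 hours after dose 1. Protocol 4.3.1 has the next infusion held after certain attributable severe events or a severe allergic reaction. A subject who reacts, stops or dies in that window leaves the set.

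The two clocks mean that a correctly enrolled subject can be dropped automatically, while one who missed the enrollment window can be approved back in.

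In the Persistence/Clearance comparison the dose condition falls on one side only. If early stoppers do worse than others, the active groups look better than placebo with no drug effect at all.

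**Working it through.** **1. The plan's own figure.** Inputs from SAP 2.2.4: 80% versus 30% response, 2:1 allocation, one-sided Fisher's exact test at 0.05, and 42 × 0.9 = 37.8, about 38. Power is the sum, over all pairs of responder counts that Fisher's test rejects, of the product of the two binomial probabilities.

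| Active : placebo | Total | Power |
|---|---|---|
| 25 : 13 | 38 | 87.8% |
| 26 : 12 | 38 | 86.3% |
| 24 : 12 | 36 | 84.4% |
| 23 : 11 | 34 | 82.1% |
| 22 : 11 | 33 | 79.7% |

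The claim of at least 80% reproduces at 38. Falling below it takes about 38 − 33 = 5 further exclusions, or 5/38 = 13%.

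**2. Which SAP set matches the powered set?**

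| Set | Dose rule | Baseline SAB required |
|---|---|---|
| Protocol MITT | at least 1 | yes |
| SAP ITT | at least 1 | no |
| SAP Per Protocol MITT | at least 4 initial | yes, counted from first dose |

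None does. The SAP ITT can include subjects enrolled on a rapid test whose culture was negative, although Protocol 7.7.1 requires conventional culture confirmation for efficacy analyses.

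**3. The clocks.** Take a subject whose only positive culture was drawn 71 hours before randomization and who is dosed 2 hours after it. The subject is eligible (71 ≤ 72) but has no baseline SAB under the SAP (71 + 2 = 73 > 72). Only a subject whose sole positive culture falls in that gap is affected.

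**4. One-sided selection (Persistence/Clearance).** Let p be the response rate among all dosed subjects, the same in both arms (no drug effect), and e the share stopping before dose 4, all assumed non-responders. Restricting active to four doses gives p/(1 − e); placebo stays at p. The documents do not give e, so a range is assumed.

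| p | e = 5% | e = 10% | e = 15% |
|---|---|---|---|
| 30% | +1.6 points | +3.3 | +5.3 |
| 70% | +3.7 points | +7.8 | +12.4 |

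For example, 0.70/0.90 = 77.8%, which is 7.8 points too high. With about 25(1 − e) active and 13 placebo subjects, the actual one-sided Fisher error at p = 70% is 6.5% for e = 10% and 9.8% for e = 15%, against 2.4% at 25:13 without selection and 5% nominal. At p = 30% it stays below 5% (3.7% at e = 10%). The real subgroups would be smaller, so these figures show direction and rough size only.

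**5. Two-sided selection (Per Protocol MITT).** On the same assumptions the spurious difference is p/(1 − e_active) − p/(1 − e_placebo). It is zero when the shares are equal. At p = 30% with 10% active and 5% placebo it is 33.3% − 31.6% = +1.8 points (1.75 before rounding). With 0% active and 10% placebo it is −3.3 points. The direction is not fixed.

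**The case against.** The SAP keeps a one-dose efficacy analysis of Phase 2a active against placebo (ITT, listed as Efficacy Population 1) and names no key set, so a reader who infers that the dosed randomized comparison has gone would be wrong. That stands. What is missing is the one-dose set restricted to baseline SAB.

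A reader might also infer that the losses are hidden. They are not: SAP 3.3.1 reports early termination of study drug with reasons among all randomized subjects by arm, SAP 3.3.3 summarizes reasons for exclusion from the Per Protocol MITT, and Section 6 discloses the changed definitions. The residual fault is that the 3.3.3 percentages for that set use subjects with at least four doses as the denominator, which leaves out those lost to the dose rule.

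The four-dose rule of SAP 3.2.2 covers both arms, treatment is blinded, the window is about 18 hours in directly observed inpatients, and exclusions are settled before database lock. That supports saying that the set could bias the comparison, not that it does.

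The clock has no evident direction: it acts before dosing and equally in both arms. Dosing should follow randomization quickly, and a positive Day 1 culture drawn before the first dose would rescue the subject. Protocol 9.1 sets no window for baseline SAB, so choosing the randomization clock rests on consistency with eligibility.

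For Persistence/Clearance, the PK-sample condition does not itself remove early failures: Protocol 7.9 takes samples at designated sites and the first is pre-dose. It does let the groups differ by site. These groups are split on phage recovery 3 hours after the first dose, so matching placebo would not make the comparison a randomized one.

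No formal testing is planned (SAP 3.1.4), but between-arm p-values are (SAP 3.4.1), and readers will set them beside the power claim.

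**Conclusion.** The point holds in three parts.

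- The powered population is absent from the SAP, and the nearest replacement adds a post-randomization condition that could bias the comparison if stopping before dose 4 differs by arm or relates differently to outcome.
- The two 72-hour clocks disagree, and individual approval has no stated criterion.
- The Persistence/Clearance comparison removes early stoppers from active only. Under the assumed 5% to 15% of non-responding early stoppers, this inflates the active rate by 1.6 to 5.3 points at a true rate of 30% and 3.7 to 12.4 points at 70%.

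It would be tempting to conclude that the trial is underpowered. The documents do not support that: power is 86% to 88% at 38, and nothing in them points to a fall to about 33. Nor do they give the share receiving one to three doses, so the actual bias cannot be derived.

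**What to change.** Before database lock:

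- **SAP 3.2.2:** analyze Day 12 clinical response in the protocol MITT (at least one dose, culture-confirmed baseline SAB). Keep the four-dose set as a labelled sensitivity analysis beside the ITT analysis. The sample-size text then needs no change.
- **SAP 3.1.2:** use one 72-hour clock, counted from randomization to match eligibility, and replace individual approval with a fixed rule applied blinded.
- **SAP 3.4 and 3.6:** apply the same four-dose and PK-sample conditions to the placebo comparator, and label the Persistence/Clearance comparison exploratory and non-randomized.
- **SAP 3.3.3:** use all randomized subjects as the denominator for population counts and show the planned exclusion reasons by arm.

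The cost is SAP wording and one population flag on data already collected. The estimate may be slightly less favorable, and the matched placebo group will be smaller than the roughly 14 randomized to placebo in Phase 2a (42/3).

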### 3.2.3 Phage Persistence and Clearance Population (Efficacy Population 3)

All subjects in Phase 1b and Phase 2a who have at least 1 PK sample drawn and received at least 4 initial doses of study drug will be divided into one of the following:

- Phage Persistence Population: defined as viable phage recovered at 3 hours post first administration of study drug
- Phage Clearance Population: defined as viable phage no longer recovered at 3 hours post first administration of study drug

Phage Persistence and Phage Clearance Population will be reported by the Sponsor separately. Subject lists for Phage Persistence Population and Phage Clearance Population will be provided by Sponsor for analysis.

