1.1.2 Phage as Antimicrobials

1.1.2.1 Mechanisms of action of phages

Figure 1. Lytic Cycle of Bacteriophages

Schematic representation of virulent phage infection, replication, and lysis of bacterial host cells.

DNA = deoxyribonucleic acid.

Source: Barbu EM, Cady KC, Hubby B. Phage therapy in the era of synthetic biology. *Cold Spring Harb Perspect Biol.* 2016;8(10):a023879

1.1.3 *Staphylococcus aureus* Phage Product, AP-SA02

Based on a comprehensive series of in vitro and in vivo studies assessing antimicrobial potential and bioavailability, AP-SA02 is an optimized product comprised of lytic phages with desirable therapeutic properties. In addition to infecting over 95% of SA clinical isolates, AP-SA02 is highly selective for SA, active against SA biofilms, viable in relevant biological fluids, and is cooperative with current standard of care antibiotics. Please see the Investigator's Brochure for details.

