**Table 1. National Early Warning Score 2 Scoring System**

Physiological parameter	3	2	1	Score 0	1	2	3
Respiration rate (per minute)	≤8		9–11	12–20		21–24	≥25
SpO 2 Scale 1 (%)	≤91	92–93	94–95	≥96			
SpO 2 Scale 2 (%)	≤83	84–85	86–87	88–92 ≥93 on air	93–94 on oxygen	95–96 on oxygen	≥97 on oxygen
Air or oxygen?		Oxygen		Air			
Systolic blood pressure (mmHg)	≤90	91–100	101–110	111–219			≥220
Pulse (per minute)	≤40		41–50	51–90	91–110	111–130	≥131
Consciousness				Alert			CVPU
Temperature (°C)	≤35.0		35.1–36.0	36.1–38.0	38.1–39.0	≥39.1	

Note: **CVPU** = Confusion, Voice, Pain, Unresponsive; SpO2 = oxygen saturation. SpO2 Scale 2 (%) is meant to be used for specific population-COPD subjects with hypercapnic respiratory failure.

Time to reach a NEWS2 score ≤2 maintained for at least 24 hours or hospital discharge (whichever comes first) will be analyzed.

Time-to-event (days) = Censoring date/event date – date of first dose of study drug + 1

The Kaplan-Meier method will be used to estimate the 25%, median and 75% times. The hazard ratio, 95% confidence interval (CI) of hazard ratio, and p-value from Cox regression model will be provided to compare AP-SA02 and placebo. Cox regression will include treatment (AP-SA02 and placebo) as factor. All assessments from scheduled and unscheduled visits will be included in the time-to-event analysis. Censoring rules for the endpoint are summarized in [Table 2](#).

The Kaplan-Meier plot of time to reach a NEWS2 score  $\leq 2$  maintained for at least 24 hours or hospital discharge (whichever comes first) will be provided.

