Clinical improvement or response (meets all criteria on [Table 2](#) in [section 7.3 of protocol](#)) at TOC for study drug (Day 12), TOC for BAT (7 days  $\pm 1$  day] after the end of BAT) and EOS (28 days after the end of BAT) will be assessed by both investigator and Clinical Efficacy Adjudication Committee (CEAC).

Based on both investigator and CEAC assessments, proportion of subjects who experience clinical improvement or response will be provided. Chi-square test p-value will be provided for clinical improvement or response to compare AP-SA02 and placebo.

The proportions of responders (including clinical improvement or response) will be plotted by AP-SA02 and placebo at TOC for study drug (Day 12), TOC for BAT (7 days [ $\pm 1$  day] after the end of BAT) and EOS (28 days after the end of BAT) by both investigator and CEAC.

Microbiological outcome at Day 5, Day 7, TOC for study drug (Day 12), TOC for BAT, and EOS will be determined programmatically based on blood culture results tested by local microbiology laboratories per [Table 3](#) as 1 of the outcomes: Eradication, Presumed eradication, Persistence, Presumed persistence, Recurrence. The microbiological outcome at Day 5, Day 7, TOC for study drug (Day 12), TOC for BAT, and EOS will be summarized with counts and percentages of subjects based on categories in [Table 3](#).

The Chi-square test p-value will be provided for the counts of microbiological eradication (including presumed eradication) and microbiological persistence (including presumed persistence) compare AP-SA02 and placebo.

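### SAP 3.4 and 3.6 set AP-SA02 subjects, split by phage recovery 3 hours after dosing, against unsplit placebo, with no exemption from the p-values and no label as non-randomised

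*SAP*

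**What the plan says.** SAP 3.2.3 defines Efficacy Population 3 by one measurement after the first dose. One group is "Phage Persistence Population: defined as viable phage recovered at 3 hours post first administration of study drug"; the other is "Phage Clearance Population: defined as viable phage no longer recovered at 3 hours post first administration of study drug". Those eligible are subjects "who have at least 1 PK sample drawn and received at least 4 initial doses of study drug will be divided" between the two. PK samples are drawn only at designated, qualified PK sites (Protocol 7.9; SAP Appendix A, note gg).

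SAP 3.4 plans "Phase 2a Persistence vs Phase 2a Clearance vs Phase 2a placebo" and a pooled version that adds Phase 1b without Cohort 1. The comparator is not restricted in the same way: "Phase 2a placebo includes Phase 2a placebo in the ITT population". ITT needs one dose only (SAP 3.2.1). SAP 3.6 repeats the scheme for the pharmacodynamic endpoints.

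SAP 3.4.1 attaches inference to the endpoints, for example "Chi-square test p-value will be provided for clinical improvement or response to compare AP-SA02 and placebo", and for time-to-event endpoints a hazard ratio and "p-value from Cox regression model will be provided to compare AP-SA02 and placebo", with treatment as the only factor. No sentence in 3.4, 3.4.1 or 3.6 exempts Population 3 or says whether its p-values are pairwise or three-group. SAP 3.1.4 rules out formal testing. SAP 6 discloses the population and its analyses as additions to the protocol plan.

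**The concern.** Randomisation balances the whole AP-SA02 arm against placebo. It does not balance a part of that arm chosen by what was found in blood after dosing. Nothing in the plan identifies the placebo subjects who would have persisted or cleared, so each part is set against a placebo group of mixed prognosis.

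This matters if 3-hour recovery goes with prognosis. One possible route is bacterial load: the Protocol 1.1.2.1 figure caption ("Schematic representation of virulent phage infection, replication, and lysis of bacterial host cells") describes phage multiplying in its host. That is an inference; no document reports such a link. In the pooled version, phase and dose cohort are further routes, since SAP 3.4 itself labels the two phases uncomplicated and complicated SAB.

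Selection adds to this. The split groups need a PK sample and at least 4 doses, while placebo subjects need 1 dose at any site. A reader given a small p-value from an efficacy population would take it as evidence about the drug.

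**Working it through.** **Inputs from the documents.** Phase 2a has 42 subjects at 2:1, so 28 active and 14 placebo; planning placebo response is 30% and the target difference 50 points (SAP 2.2.4). SAP 3.4.1 specifies a chi-square test.

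**Assumed, because the documents do not say.** The fraction with phage recovered (one half, then uneven splits) and the gap in response between the two parts (0, 20, 30 or 40 points). Also a two-sided nominal 0.05, the uncorrected Pearson test, and pairwise comparison.

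**Step 1, the plan's own figure.** Exact power of Fisher's test, one-sided 0.05, 80% against 30%, at 25:13 (38 MITT subjects) is 87.8%. The stated minimum of 80% is met, so the inputs are read correctly.

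**Step 2, an inert drug.** Let the parts respond at 0.30 − g/2 and 0.30 + g/2. With g = 0.40 these are 10% and 50%, and the arm average is (14×0.10 + 14×0.50)/28 = 0.30, the placebo rate. Any difference from placebo then says nothing true about the drug.

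**Step 3, the test.** χ² = Σ(O−E)²/E, significant above 3.84. Example: 7/14 against 2/14 has expected counts 4.5 and 9.5 per group, so χ² = 2×2.5²/4.5 + 2×2.5²/9.5 = 2.78 + 1.32 = 4.09, p = 0.043.

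**Step 4, exact enumeration.** With q₁(b) and q₂(b) the chances that each part is significant given b placebo responders,
P(at least one) = Σ P(b) × [1 − (1 − q₁(b))(1 − q₂(b))].
False benefit counts only significant results in favour of AP-SA02.

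| Gap (points) | Response in the parts | 14/14: either part differs | 14/14: false benefit | Whole arm vs placebo | 10/10: either part differs |
|---|---|---|---|---|---|
| 0 | 30% / 30% | 9.4% | 4.6% | 5.4% | 8.4% |
| 20 | 20% / 40% | 17.1% | 8.0% | 5.2% | 14.4% |
| 30 | 15% / 45% | 27.1% | 12.1% | 4.9% | 22.3% |
| 40 | 10% / 50% | 42.0% | 17.6% | 4.6% | 33.9% |

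The 10/10 column keeps 14 placebo and allows for active subjects lost to the PK-site and 4-dose rules; the true number is unknown.

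**Step 5, other settings.** At the 20-point gap and 14/14, single comparisons reject in 9.3% and 8.4%. A three-group chi-square rejects in 16.4% and 56.1% at 20 and 40 points. At 40 points, uneven splits give 45.5% (better part 19 of 28) and 41.6% (better part 9 of 28). With 50% response and 14/14 the 40-point figure is 34.3%.

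**Step 6, pooling.** At planned size, Cohort 2 adds 3 active and 1 placebo. Phase 1b then makes up 3/31 = 9.7% of active and 1/15 = 6.7% of placebo. An assumed 40-point difference between phases would bias the unstratified whole-arm contrast by 0.40 × 3.0 = 1.2 points. If Phase 1b grew to its limit of 20 (16 after Cohort 1, or 12 and 4 at 3:1), the shares are 12/40 = 30.0% and 4/18 = 22.2%, a bias of 0.40 × 7.8 = 3.1 points. Pooling is minor beside the split.

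**The case against.** The strongest reply is that the plan does not test this. SAP 3.1.4 rules out formal testing, SAP 3.4 says the population is summarised in three groups, and the p-values are worded as AP-SA02 against placebo. A reader might infer that pairwise tests of each part against placebo are prespecified. They are not; the SAP is silent on their form. What remains is that 3.4.1 and 3.6 call for p-values and hazard ratios and do not exempt this population, so a programmer following the text could produce them.

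A reader might also infer that the trial's efficacy conclusion rests on this split. It does not: whole-arm ITT and Per Protocol MITT comparisons are planned, exposure against efficacy is a listed endpoint, and the addition is disclosed. Nor do the documents say the contrast will set a dose; the Phase 2a dose rests on safety and tolerability.

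The rates depend on assumed gaps, and the either-part figures include results where the drug looks harmful. Both points stand, which is why false benefit is shown separately. It would also be wrong to count Persistence against Clearance rejections as false positives: under these assumptions the two parts truly differ, so rejecting there is correct detection.

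**Conclusion.** The point holds as a confounded, unlabelled contrast for which inferential output is not switched off. With an inert drug and 14/14/14 subjects at 30% response, gaps of 20 to 40 points raise the chance of at least one nominally significant difference from placebo from 9.4% to between 17% and 42%, and of a false benefit from 4.6% to between 8% and 18%. With 10/10 active subjects the either-part range is 14% to 34%. The whole-arm comparison stays near 5% at 14/14, so the excess comes from the split.

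These figures illustrate what happens if recovery is prognostic; they do not estimate this trial's error rate. With no prognostic link, the excess over 5% is only that of making two comparisons. The non-randomised nature of the contrast and the unequal entry rules do not depend on any assumed gap. The point is worth correcting before database lock, but it does not touch the whole-arm analyses.

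**What to change.** In SAP 3.4 and 3.6:

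- State that no p-value or hazard ratio is produced for Persistence or Clearance against placebo, and that AP-SA02 against placebo rests on the whole randomised arms within phase.
- Report Persistence against Clearance among AP-SA02 subjects only, as a descriptive, non-randomised exposure-response summary with estimate and 95% CI. Present it by phase, or stratified by phase where phases are pooled, and show baseline characteristics by group.
- Keep further covariate adjustment minimal. At 30% response, 28 active subjects give about 28 × 0.30 = 8 responders, too few for a model with several covariates.
- Reconcile 3.2.3 with 3.4. Section 3.2.3 divides all subjects on study drug, and 3.2.2 uses study drug to mean placebo or phage, so read literally a placebo subject with a PK sample and no phage falls into Clearance. Section 3.4 keeps placebo as a separate group.

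The cost is SAP wording and fewer outputs; visits and data collection do not change. What is lost is a p-value against placebo for a hypothesis-generating subgroup.
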